### **9.6.7. Acne**

Visual analog scales (VAS) were used to assess the subject's perception of severity of acne in all female subjects, scored on a 100 mm visual analog scale, from 0 mm (no symptoms) to 100 mm (very severe symptoms). Observed and change from baseline values in VAS scores for acne will be summarized descriptively by visit and treatment group. Mean ( $\pm$ SEM) observed values at each visit will be summarized in line graphs by treatment group. Similar graphs will be presented for the change from baseline values.

The change from baseline to Week 24 in VAS score for acne will be analyzed using an ANCOVA model as described in Section 9.2.1 (with the exception of sex as a stratification factor). Descriptive statistics and LS means for change from baseline to Week 24 in the VAS score for acne will be presented by treatment group along with the LS-mean treatment difference, 95% confidence intervals, and p-value.

### **9.6.8. Bone Markers**

Serum osteocalcin and serum bone-specific alkaline phosphatase are bone marker measurements to assess bone formation. Serum C-terminal telopeptide (CTx) and urine N-terminal telopeptide (NTx) are bone marker measurements to assess bone resorption. Observed and change from baseline values in these bone markers will be summarized using descriptive statistics by treatment group and visit. The change from baseline to Week 24 for each of these bone marker

parameters will be analyzed using an ANCOVA model as described in Section 9.2.1. Descriptive statistics and LS means for change from baseline to Week 24 in each of the bone marker parameters will be presented by treatment group along with the LS-mean treatment difference, 95% confidence intervals, and p-value. If there are a sufficient number of postmenopausal women with bone marker values, all of the above analyses will be repeated in this subset of subjects.

### **9.6.9. Glucocorticoid Dose Regimen**

In subjects on hydrocortisone alone at baseline with a dosing frequency of more than once per day (eg, 5x/day, QID, TID, or BID), a responder is defined as a subject whose dose is reduced by at least one dosing instance per day at Week 24. For example, responders include subjects who reduce from QID to TID (or BID or QD), TID to BID (or QD), or BID to QD, from baseline to Week 24. The number and percentage of subjects meeting this responder definition at Week 24 will be summarized by treatment group. A shift table of hydrocortisone dosing frequency from baseline to Week 24 will also be presented. The rows of the shift table will reflect the dosing frequency at baseline and the columns will reflect the dosing frequency at Week 24. The number and percentage of subjects in each shift category will be displayed in the table; percentages will be based on the number of subjects included in the table.

In subjects on a prednisone or equivalent (eg, methylprednisolone or prednisolone) or a hydrocortisone plus prednisone (or equivalent) regimen at baseline, a responder is defined as a subject who switches to a hydrocortisone alone regimen at Week 24 (i.e, a subject who stops taking prednisone or equivalent prior to the Week 24 visit and is on a hydrocortisone-only regimen at Week 24). The number and percentage of subjects meeting this responder definition at Week 24 will be summarized by treatment group.

In subjects on a dexamethasone regimen at baseline, a responder is defined as a subject who switches to a hydrocortisone alone regimen at Week 24. The number and percentage of subjects meeting this responder definition at Week 24 will be summarized by treatment group.

In subjects on a dexamethasone regimen at baseline, a responder will also be defined as a subject who switches to a regimen that does not contain dexamethasone at Week 24. The number and percentage of subjects meeting this responder definition at Week 24 will be summarized by treatment group.

The achievement of (1) response for hydrocortisone alone dosing frequency reduction; (2) switching from prednisone (or equivalent) regimen to hydrocortisone alone regimen at Week 24; (3) switching from a dexamethasone regimen to hydrocortisone alone regimen at Week 24; and (4) switching from a dexamethasone regimen to a dexamethasone-free regimen at Week 24 (as defined for each of the responder analyses described above) will be analyzed using a CMH test as described in Section 9.2.2. The CMH test will compare treatment groups and will include stratification factors used in the randomization. Subjects who are missing Week 24 data will be omitted from the analysis.

### **9.7. Examination of Subgroups**

The following subgroups have been pre-planned and will be used to examine consistency of effect for the primary efficacy endpoint:

- Region (OUS versus US)
- Glucocorticoid type – dexamethasone use (subjects on dexamethasone at baseline versus subjects not on dexamethasone at baseline)
- Glucocorticoid type – hydrocortisone vs. synthetic glucocorticoids (subjects on hydrocortisone alone versus subjects on prednisone [or equivalent] or dexamethasone)
- Sex (male versus female; based on the eCRF)
- BMI ( $< 30 \text{ kg/m}^2$  vs.  $\geq 30 \text{ kg/m}^2$ )
- Race
- Ethnicity
- Age ( $< 65$  years vs.  $\geq 65$  years)
- Baseline total daily glucocorticoid dose ( $<20 \text{ mg/m}^2/\text{day}$  versus  $\geq 20 \text{ mg/m}^2/\text{day}$ ; based on the eCRF)

If any of these categories are sparse in number of subjects (e.g.,  $<15$ ), the categories with the fewest number of subjects may be collapsed until there are at least 15 subjects or the subgroup analysis may be omitted entirely. The decision to omit a subgroup analysis will be justified in the CSR. Each subgroup will be analyzed separately using an ANCOVA model that is similar to the model used in the primary analysis of the primary endpoint (as described in Section 9.2.1), with the addition of the subgroup variable added as a main effect term and an interaction term between treatment group and the subgroup variable. Note that for the sex, baseline glucocorticoid type, and baseline total daily glucocorticoid dose ( $<20 \text{ mg/m}^2/\text{day}$  versus  $\geq 20 \text{ mg/m}^2/\text{day}$ ), the values reported on the eCRF will be used in the model instead of the values reported as stratification factors in the IRT. Nominal two-sided p-values for comparing treatment groups and the associated 95% confidence intervals will be reported in summary tables and a forest plot, with p-values for the interaction term between treatment groups and subgroup variables will be presented.

## 10. EFFICACY – OL PERIOD

The efficacy endpoints and planned analysis methods for the OL period are described below. The OL Period Safety Analysis Set will be used for all efficacy analyses and descriptive statistics in the OL period. Unless otherwise noted, the below summaries will follow the treatment group and baseline definitions defined for the OL period (as described in Section 6). Missing data will not be imputed for any of the below analyses and summary displays will start with Month 7 as the first postbaseline visit, unless otherwise specified.

### 10.1. Glucocorticoid Total Daily Dose

Descriptive statistics will be presented by treatment group and visit for the glucocorticoid total daily dose ( $\text{mg}/\text{m}^2/\text{day}$ ) observed, change from OL baseline, and percent change from OL baseline values to Month 12. Mean ( $\pm\text{SEM}$ ) values of the glucocorticoid total daily dose ( $\text{mg}/\text{m}^2/\text{day}$ ) at each visit will be summarized in line graphs by treatment group. Similar graphs will be presented for the change from OL baseline and percent change from OL baseline. These summaries will be presented for both the glucocorticoid total daily doses *without* the derivation of 0 for loss of androstenedione control as well as the glucocorticoid total daily doses *with* the derivation of 0 for loss of androstenedione control (only for subjects with a decrease in glucocorticoid total daily dose).

The above summaries will be repeated for the change from baseline (Day 1) to Month 12 in glucocorticoid total daily dose. For the summary tables, the change from baseline to each postbaseline visit will start with Month 7 and conclude at Month 12. Figures of the mean ( $\pm\text{SEM}$ ) observed, change from baseline, and percent change from baseline glucocorticoid total daily dose values (with and without the derivation of zero for loss of androstenedione control) will include all visits from baseline (Day 1) to Month 12.

The descriptive statistics summary table will also be produced for the glucocorticoid total daily dose ( $\text{mg}/\text{day}$ ) observed, change from OL baseline, and percent change from OL baseline values (with and without the derivation of 0 for loss of androstenedione control).

Similar to the responder analysis defined in Section 9.4.2, a physiologic glucocorticoid dose responder will be defined as the achievement of a reduction in glucocorticoid total daily dose to physiologic levels ( $\leq 11 \text{ mg}/\text{m}^2/\text{day}$  hydrocortisone equivalent adjusted for BSA) at a visit, while androstenedione is adequately controlled at  $\leq 120\%$  of baseline or  $\leq \text{ULN}$  for age and sex, respectively, at that specific visit. Androstenedione control will be assessed based on the androstenedione values at baseline and each respective OL period visit through Month 12 following the same method as described in Section 6.3.3. Descriptive statistics will be presented by treatment group for the number and percentage of subjects classified as responders and non-responders at each visit in the OL period.

### 10.2. Hormone Measurements

Descriptive statistics will be presented by treatment group and visit for the observed and change from OL baseline values for the following hormone measurements in the OL period: ACTH, 17-OHP, androstenedione, total testosterone, LH, FSH, progesterone, and SHBG. For visits where the hormone measurement is collected more than once (eg, Month 12), each visit will be presented with the pre- and post- morning glucocorticoid dose hormone values at that visit. All

summaries of testosterone and progesterone will be stratified by sex. Summaries of FSH, LH, and SHBG will also be stratified by sex as well as by combined sexes.

Mean ( $\pm$ SEM) values of the above hormone measurements at each visit in the OL period will be summarized in line graphs by treatment group. For visits where the hormone is collected more than once, each visit will be presented with the pre- and post-morning glucocorticoid dose hormone values on separate plots. Similar graphs will be presented for the changes from OL baseline.

The above summaries will be repeated for the change from baseline (Day 1) to Month 12 in each of the hormone parameters.

Shifts from OL baseline to Month 12 in gonadotropin values (LH and FSH) will be presented in shift tables by sex as well as by combined sexes. Postmenopausal women will be excluded from the shift tables. Each shift table will have four rows and four columns, with rows reflecting the reference range category at OL baseline (low, normal, high, missing), and columns reflecting the reference range category at Month 12 (low, normal, high, missing). A “Total” row and “Total” column will also be included. The number and percentage of subjects in each shift category will be displayed in the table; percentages will be based on the number of subjects included in the table.

A responder definition for the normalization of testosterone in female subjects will be defined as female subjects with testosterone levels that are greater than or equal to 1.2x ULN (based on age) at OL baseline and decrease to within the normal range at any postbaseline visit, based on the average of the testosterone values at the applicable visit. Descriptive statistics will be presented by treatment group for the number and percentage of female subjects classified as responders and non-responders at each visit in the OL period.

A responder definition for the normalization of progesterone in female subjects of child-bearing potential not on hormonal contraceptives will be defined as female subjects with a progesterone level  $>0.6$  ng/mL at OL baseline and decrease to a progesterone level  $<0.6$  ng/mL at any postbaseline visit thereafter. The average of the progesterone levels will be used at visits where more than one hormone sample is collected. This analysis will be restricted to female subjects who are of childbearing potential and are not on hormonal contraceptives. Descriptive statistics will be presented by treatment group for the number and percentage of female subjects classified as responders and non-responders at OL baseline and each visit thereafter in the OL period.

A responder definition for the normalization of LH will be defined as subjects with abnormal LH levels at OL baseline (defined as  $<$  LLN or  $>$  ULN) and achieve normalization at Month 12 in male subjects based on pre-GC dose levels. The number and percentage of subjects meeting this responder definition at Month 12 will be summarized by treatment group. This responder definition and summarization will also be repeated for FSH.

A responder definition for the ratio of androstenedione to testosterone (A4/T) in male subjects will be defined as male subjects who have A4/T greater than or equal to 0.5 (based on the pre-glucocorticoid dose values for androstenedione and testosterone) at OL baseline and who achieve A4/T less than 0.5 at any postbaseline visit thereafter. Descriptive statistics will be presented by treatment group for the number and percentage of male subjects classified as responders and non-responders at OL baseline and each visit thereafter in the OL period.

In addition to the serum hormone measurement summaries described above, urine androgen metabolite levels, including androsterone and etiocholanolone (corrected for urine creatinine), will be summarized with descriptive statistics by visit and treatment group. Summary tables will include observed and change from OL baseline values for each urine androgen parameter.

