^j Collect blood sample for hormone measurements (adrenocorticotrophic hormone [ACTH], 17-hydroxyprogesterone [17-OHP], cortisol, androstenedione, testosterone, luteinizing hormone [LH], follicle stimulating hormone [FSH], progesterone, plasma renin activity [PRA; measured upright], and sex hormone binding globulin [only for the second blood sample collected at Months 12, 13, and 18]) in the morning approximately 2 to 3 hours after the morning glucocorticoid dose. At Month 12, Month 13 (only for re-randomized subjects), and Month 18/early termination, collect additional blood sample prior to morning glucocorticoid dose. The second blood sample should be collected prior to 1100 hours. Subjects not on a morning glucocorticoid should still have 2 morning blood samples taken (with the glucose tolerance test and/or before and after the morning study drug dose). The last dose of glucocorticoid taken prior to the first blood sample should be documented.

^k Urine sample should be collected by the subject at home starting at midnight the night before the visit until the first morning void after awakening for the day using a container provided to the subject and brought to the study center.

^l Collect blood sample after subject fasting at least 8 hours for glucose, insulin, total cholesterol, low-density lipoprotein, high-density lipoprotein, triglyceride, and glycated hemoglobin (HbA1c).

^m Collect blood sample for osteocalcin, bone-specific alkaline phosphatase, and C-terminal telopeptide (CTx) and collect urine sample (fasting, after first morning void) for N-terminal telopeptide (NTx).

ⁿ After an overnight fast (minimum of 8 hours), collect blood samples prior to (within 30 minutes) and approximately 2 hours after 75-gram glucose load (only in subjects without diabetes mellitus).

^o For males only. Testicular ultrasound is not required during an early termination visit if the subject had a testicular ultrasound within 3 months prior.

^p Not required during an early termination visit if the subject had a DXA within 3 months prior.

^q For female subjects only. Menstrual questionnaire only for females of childbearing potential not on hormonal or intrauterine device contraceptives.

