### **6.3.2. Baseline Definition for Analyses of OL Period Data**

Two baselines will be defined for analyses of data from the OL period. For all efficacy summaries in the OL period, the Week 24 assessments collected prior to the first dose of study drug in the OL period will serve as one of the baseline values for assessments through Month 12 of the study. This baseline will be referred to as the “OL baseline” throughout this document. Unless otherwise noted, all efficacy summaries will be repeated using the study baseline (as defined in Section 6.3.1). For both the OL baseline and study baseline, if the respective Week 24 or Day 1 value is not available, then the last measurement collected prior to study drug in each period will serve as baseline. Specifically, for the OL period, if the Week 24 value is not available, then the last measurement collected prior to study drug in the OL period will serve as baseline as long as the last non-missing measurement is not the study baseline value. For assessments that are performed every 6 months, if the Week 24 assessment is not available then the OL baseline and postbaseline values will not be included in the summary.

Body composition assessments obtained within 2 weeks after Week 24 may serve as the OL baseline if needed. Bone mineral density and testicular ultrasound assessments obtained within 1 month after Week 24 may serve as the OL baseline value if needed, as these parameters are not expected to change to a degree that could be clinically detected over this time frame.

Note that for hormone parameters that are collected both pre- and post-GC dose, OL baselines will be defined as the last pre- or post-GC dose value available prior to study drug dosing at Week 24 for all pre- and post-GC postbaseline values (after Week 24), respectively, where a change from OL baseline calculation is necessary, unless otherwise specified.

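### The open-label responder rules for A4/T, testosterone and progesterone (SAP 10.2) compare Week 24 with Months 7 to 10 on different sample types, so by-visit response there is mismatched or, for A4/T, may not be computable

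*SAP*

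**What the plan says.** **Responder rules (SAP 10.2).**

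- A4/T, men: to enter, a man must "have A4/T greater than or equal to 0.5 (based on the pre-glucocorticoid dose values for androstenedione and testosterone) at OL baseline". The rule then counts men who were above that entry level "at OL baseline and who achieve A4/T less than 0.5 at any postbaseline visit thereafter", naming no sample type for the later value. The display is the "number and percentage of male subjects classified as responders and non-responders at OL baseline and each visit thereafter in the OL period".
- Testosterone, women: entry is a level "greater than or equal to 1.2x ULN (based on age) at OL baseline". Response is a "decrease to within the normal range at any postbaseline visit, based on the average of the testosterone values at the applicable visit". Responders are tabulated at each open-label visit.
- Progesterone, women of childbearing potential not on hormonal contraceptives: entry is above 0.6 ng/mL at open-label baseline, and response is below 0.6 ng/mL at any later visit. Where a visit has more than one sample, the average is used.

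**Baseline (SAP 6.3.2).** The open-label baseline is set as follows: "the Week 24 assessments collected prior to the first dose of study drug in the OL period will serve as one of the baseline values".

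**Sampling.** Protocol 9.3.2 and the footnotes to Tables 1 and 2 schedule one hormone sample per visit, 2 to 3 hours after the morning GC dose. They add a pre-GC sample at only some visits. Week 24 is one of them. From Month 7 on, the Table 2 footnote reads: "At Month 12, Month 13 (only for re-randomized subjects), and Month 18/early termination, collect additional blood sample prior to morning glucocorticoid dose". Months 7, 8, 9 and 10 are not listed.

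**The concern.** A threshold-crossing rule assumes that the same quantity is measured before and after. Here the baseline is a pre-GC value (A4/T) or a pre/post mean (testosterone, progesterone), while the value at Months 7 to 10 can only be post-GC. If post-GC values are lower, a subject whose hormones have not changed can cross the threshold because of when the sample was drawn.

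The timing makes this awkward. Month 7 comes after a month of stable GC dosing and is the first on-drug visit for subjects who had been on placebo, so a sampling artefact there could look like an early drug effect. At Month 12 the sample types match again, and an artefactual response could then seem to be lost. The open-label period has no concurrent placebo group against which to judge either pattern.

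**Working it through.** The plan states no figure for these rules, so there is none to reproduce. The check compares the schedule with the rules, then works out who could be misclassified.

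**Step 1. Samples against rules**

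| Visit | Samples | A4/T | Testosterone, progesterone |
|---|---|---|---|
| Week 24 (baseline) | pre and post | pre-GC | mean of pre and post |
| Months 7, 8, 9, 10 | post only | post-GC, or no value | single post-GC value |
| Month 12 | pre and post | pre-GC available | mean of pre and post |

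Four of the five open-label visits are unmatched; Month 12 is paired.

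**Step 2. Does other text repair it?** SAP 6.3.2 pairs like with like "for all pre- and post-GC postbaseline values (after Week 24), respectively", but only where a change from open-label baseline is calculated, and it gives way to more specific text. A responder threshold is not a change score, so the pairing does not reach these rules. Neighbouring rules avoid the problem by using visits with both samples: the double-blind A4/T and testosterone rules in SAP 9.6.1 use Week 24, and the open-label LH and FSH rule uses Month 12 on pre-GC values.

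**Step 3. Unchanged subject, A4/T.** Let r be the post-GC A4/T ratio divided by the pre-GC A4/T ratio at the same visit. The documents do not give r; the range 1.0 to 0.5 is an assumption. The subject is falsely counted if pre ≥ 0.5 and r × pre < 0.5, that is, if the pre-GC ratio lies in [0.5, 0.5/r).

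- r = 1: no one
- r = 0.9: 0.50 to below 0.5/0.9 = 0.556
- r = 0.8: 0.50 to below 0.5/0.8 = 0.625
- r = 0.7: 0.50 to below 0.5/0.7 = 0.714
- r = 0.5: 0.50 to below 0.5/0.5 = 1.00

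**Step 4. Unchanged subject, testosterone.** Let k be post/pre for testosterone (also assumed, 1.0 to 0.5). The baseline mean is pre × (1 + k)/2 and the later value is k × pre. False response needs a mean ≥ 1.2 × ULN and a post value ≤ ULN. With post exactly at the ULN, pre must be at least 2 × 1.2 − 1 = 1.4 × ULN, so k ≤ 1/1.4 = 0.714, a within-visit fall of at least 28.6%. The affected Week 24 means run from 1.2 to (1 + k)/(2k) × ULN.

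- k = 0.9 or 0.8: no one
- k = 0.7: 1.20 to 1.7/1.4 = 1.214
- k = 0.6: 1.20 to 1.6/1.2 = 1.333
- k = 0.5: 1.20 to 1.5/1.0 = 1.50

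**Step 5. Unchanged subject, progesterone.** Entry and response share the 0.6 ng/mL threshold, so no gap absorbs a small fall. With k now post/pre for progesterone, the affected means lie between 0.6 and 0.6 × (1 + k)/(2k). At k = 0.9 the upper limit is 0.6 × 1.9/1.8 = 0.633 ng/mL; at k = 0.7 it is 0.6 × 1.7/1.4 = 0.729 ng/mL.

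**Step 6. After matching.** On one sample type an unchanged subject cannot be both ≥ 0.5 and < 0.5, both ≥ 1.2 × ULN and ≤ ULN, or both above and below 0.6 ng/mL. The false-response band is empty for every r and k.

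**The case against.** The strongest reply concerns A4/T. The double-blind rule in SAP 9.6.1 has the same syntax, with the pre-GC qualifier attached to baseline, and it is naturally read as pre-GC throughout. Read the same way, the open-label rule has no value at Months 7 to 10, nothing is imputed (SAP 10), and no unchanged man is counted as normalised. This stands as a possible reading. It removes the bias but leaves a planned by-visit table that can be filled only at Month 12, so the text still needs changing.

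A second reply is that the direction and size of the error are unproven, and that also stands. A fall after the dose is plausible. Protocol 9.3.3 describes an early-morning ACTH surge with androgen production following it. Exclusion criterion 3 sets a lower 17-OHP limit for post-GC than for pre-GC samples. But no pre/post ratio is given for androstenedione, testosterone or progesterone. If testosterone falls in step with androstenedione, r = 1 and the A4/T band vanishes; if it falls further, the error runs against response. Some subjects take no morning GC, so the dose effect does not apply to them.

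Three stronger readings are tempting, and the documents do not support them:

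- That open-label normalisation rates are inflated in both groups. This needs a ratio that the documents do not give, and for testosterone a fall of at least 28.6%.
- That the error accumulates over four visits. The displays are counts at each visit, and no ever-responder rate is clearly planned.
- That the rules violate SAP 6.3.2. That section covers change calculations only.

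**Conclusion.** The mismatch is real and follows from the schedule alone. At Months 7 to 10 the testosterone and progesterone rules, as written, set a single post-GC value against a pre/post average. The A4/T rule is either mismatched in the same way or cannot be computed.

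Whether anyone is misclassified, and how many, depends on assumed post/pre ratios. For A4/T and progesterone any fall below 1 opens a band; for testosterone the 1.2 × ULN entry threshold absorbs all falls smaller than 28.6%. The number of subjects inside these bands cannot be estimated from the documents.

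The consequence is limited. The summaries are exploratory and descriptive, with no test, and these responder definitions are not among the open-label endpoints listed in SAP 4.5. No primary or key secondary result changes. The repair is still worth making, because the rule gives a wrong or unusable by-visit result and needs no new data to correct.

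**What to change.** In SAP 10.2, name the sample type at both time points for all three rules.

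1. For by-visit displays (Months 7, 8, 9, 10 and 12), define both open-label baseline and response on post-GC values. That sample is scheduled at Week 24 and at every open-label visit. The match is close rather than exact: about 2 hours after the dose at Week 24, against 2 to 3 hours at Months 7 to 10.
2. Keep pre-GC A4/T and the pre/post averages of testosterone and progesterone for Week 24 versus Month 12 only, replacing response at any later visit with response at Month 12.

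The cost is SAP wording and programming. SAP 5.2 already analyses available data through Month 12 at the Week 24 analysis, so the change is best made before that lock.

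There are two drawbacks. By-visit post-GC A4/T will not be directly comparable with the pre-GC responder of the double-blind period. If post-GC values are lower, somewhat fewer subjects will meet the baseline threshold.
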